3.6.2 Clinical Laboratory Tests

All laboratory data will be converted to standard units during the Data Management process.

Summary statistics will be provided for laboratory values as well as their changes from baseline for all laboratory parameters by treatment group.

Counts and percentages of subjects with any post-baseline observation that is below the lower limit of normal (<LLN) or above the upper limit of normal (>ULN) will be summarized for each laboratory parameter by treatment group and total.

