2.2 Study Design

2.2.1 *Overview*

[figure not shown]
This study will be conducted at approximately 20-25 sites in the United States. The Phase 2 study of levosimendan in PH-HFpEF subjects has been designed in two phases (Figure 1). The study will recruit male and female subjects meeting identified enrollment criteria for PH-HFpEF into the lead-in open label phase to identify “responders” to levosimendan intravenous infusion of at 0.10 µg/kg/min for 24 hours \pm 30 min. Subjects that have clinically relevant responses to levosimendan will be randomized to levosimendan or placebo (1:1) and receive intermittent (weekly) study drug infusions (Week 2-5). The first 36 subjects who demonstrate a \geq 4mmHg reduction in PCWP from baseline measured at bicycle exercise (25 watts) with no more than a 10% decrease from baseline in cardiac index will be classified as a “responder” to the

lead-in levosimendan dose and be randomized to the double-blind phase of the study. Patients who do not tolerate the initial levosimendan infusion due to excessive hypotension or tachycardia will be dropped from eligibility. In the double-blinded phase, patients will be randomized to levosimendan or placebo and receive a weekly dose of study drug intravenously at $0.075 \mu\text{g}/\text{kg}/\text{min}$ for 24 hours ± 30 min and if tolerated titrated to $0.10 \mu\text{g}/\text{kg}/\text{min}$ for 24 hours ± 30 min at Week 4. The infusion rate of study drug may be decreased or interrupted as clinically warranted if the subject has hypotension, tachycardia, or signs or symptoms consistent with hypovolemia (e.g., low systolic blood pressure [SBP], decreasing urine output with rising blood urea nitrogen [BUN] and serum creatinine) Record the time of discontinuation or down titration. Patients should be monitored closely until clinically stable. See Protocol Attachment 1 for infusion rates and instructions on dose adjustments. Patients will be evaluated Week 6 to determine the efficacy and safety of levosimendan. Randomized subjects that have not received study drug weekly through Week 5 and returned for evaluation on Week 6 will be replaced to ensure 18 subjects have completed in each study group.

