3 STATISTICAL METHODOLOGY

3.1 General Considerations

3.1.1 *Study Day*

Study day will be calculated from the date of first dose of study drug (lead-in infusion). The day of the first dose of study drug will be Day 1, and the day immediately before Day 1 will be Day -1. There will be no Day 0.

3.1.2 *Definition of Baseline*

Baseline is defined as the value obtained prior to lead-in study drug infusion on Visit 1. Note: The protocol-specified visit ‘Day 0’ will be referred to as ‘Visit 1’ for analysis purposes.

3.1.3 *Analysis Visit Windows*

Post-baseline assessments will be assigned a visit number based on the study day. Analysis visit windows will be defined as below:

- Screening: ≤ 28 Days Prior to Visit 1,
- Lead-In Visit: Visit 1/Week 1/Day 1,
- Visit 2/Week 2/Day 8: Day 2 to Day 11,
- Visit 3/Week 3/Day 15: Day 12 to Day 18,
- Interim Office Visit: Between Visit 3/Week 3 and Visit 4/Week 4,
- Visit 4/Week 4/Day 22: Day 19 to Day 25,
- Visit 5/Week 5/Day 29: Day 26 to Day 32, and
- Visit 6/Week 6/Day 36: Day 33 or later.

3.1.4 *Summary Statistics*

Categorical data will generally be summarized with counts and percentages of subjects. The denominator used for the percentage calculation will be clearly defined. Continuous data will generally be summarized with descriptive statistics including n (number of non-missing values), mean, median, standard deviation, minimum, and maximum.

3.1.5 *Handling of Dropouts and Missing Data*

In cases of missing or incomplete data (e.g. adverse event [AE] and concomitant medications), the missing component(s) will be assumed as the most conservative value possible. For example, AEs with missing start dates, but with stop dates either overlapping into the treatment period or missing, will be counted as treatment-emergent, taking the worst-case approach. When partial dates are present in the data, both a partial start date and/or a partial stop date will be evaluated to determine whether it can be conclusively established that the AE started prior to the start of study drug or ended prior to the start of study drug. If the above cannot be conclusively established based on the partial and/or present dates, then the AE will be considered as treatment-emergent. Actual data values as they appear in the original eCRF will be presented in the data listings. Missing values for other variables will not be imputed and only observed values will be used in data analyses and presentation.

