3.2.4 Safety Analysis Set

The Safety Analysis Set is defined as enrolled/randomized subjects who received open-label levosimendan and/or any blinded study drug.

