3.6 Safety Assessment

Safety data will be summarized by actual treatment received (and in total for selected analyses) in the double-blind phase based on the Safety Analysis Set.

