3.6.1 Adverse Events

An AE is any untoward medical occurrence in a clinical investigation subject administered a pharmaceutical product and that does not necessarily have a causal relationship with this treatment. All AEs are collected from the time the informed consent is signed until the subject discontinues or until Week 6 (whichever is first). All AEs will be coded to system organ class and preferred term using MedDRA version 21.0. Treatment-emergent adverse events (TEAEs) are defined as AEs that start after the first dose of study drug (lead-in infusion).

TEAEs with onset during the lead-in phase and double-blind phase will be summarized separately. TEAEs that start on or after the lead-in infusion and prior to the first double-blind infusion will be attributed to the lead-in phase, while TEAEs that start on or after the first double-blind infusion will be attributed to the double-blind phase. All AEs that start prior to the lead-in infusion will be listed.

Adverse events of special interest include the following preferred terms: hypotension, atrial fibrillation, clinically significant arrhythmia, aborted resuscitated death, and stroke.

An overview of TEAEs will be provided including counts and percentages of subjects with the following:

- Any TEAEs (overall and by maximum severity)
- Any study drug related TEAEs (overall and by maximum severity)
- Any TEAEs of special interest (overall and by maximum severity)
- Any serious TEAEs (TESAEs)
- Any TEAEs leading to discontinuation of study drug
- Any TEAEs leading to discontinuation of study
- Any TEAEs leading to death

Counts and percentages of subjects will also be presented by system organ class and preferred term for each of the categories in the overview.

Listings will be presented specifically for SAEs and TEAEs leading to discontinuation of study drug.

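### By-arm counts of out-of-range laboratory values start before the first blinded infusion, so any sample taken after the open-label lead-in counts in the blinded arm and can dilute the contrast

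*SAP*

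**What the plan says.** Five statements in the SAP bear on this point.

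- **Counting rule (3.6.2).** The plan is to report "Counts and percentages of subjects with any post-baseline observation that is below the lower limit of normal" or above the upper limit. These counts "will be summarized for each laboratory parameter by treatment group and total". No start time or study phase is given.
- **Baseline (3.1.2).** "Baseline is defined as the value obtained prior to lead-in study drug infusion on Visit 1". No second baseline before the first blinded infusion is defined.
- **Grouping (3.6).** "Safety data will be summarized by actual treatment received (and in total for selected analyses) in the double-blind phase", on the Safety Analysis Set, which consists of "enrolled/randomized subjects who received open-label levosimendan and/or any blinded study drug" (3.2.4).
- **Design (2.2.1).** Subjects are recruited "into the lead-in open label phase to identify “responders” to levosimendan intravenous infusion". Only responders are then randomized, so every randomized subject, including those later given placebo, has already received open-label levosimendan.
- **Adverse events (3.6.1).** "TEAEs with onset during the lead-in phase and double-blind phase will be summarized separately". The cut-point is the first double-blind infusion.

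**The concern.** Read together, these definitions make a value post-baseline as soon as the lead-in infusion has begun, about a week before blinded treatment starts. A placebo subject whose only out-of-range value came in that interval would be reported as a placebo-arm abnormality. An adverse event arising on the same day in the same subject would be reported under the lead-in phase.

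The purpose of a by-arm laboratory table is to let a reader compare blinded levosimendan with placebo. Observations from a period when both future arms had received the same open-label drug carry no information about that comparison. They can only add to the rate in each arm, and they can make the arms look more alike. In a trial with 18 subjects per arm, safety tables are read by eye, and dilution toward no difference is the less cautious direction in which to err.

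**Working it through.** **Does anything in the SAP remove the lead-in observations?**

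| Possible safeguard | What the SAP provides |
|---|---|
| Phase split for laboratory data | None in 3.6.2; the split in 3.6.1 is written for adverse events |
| Baseline reset before blinded dosing | None; 3.1.2 has one baseline, before the lead-in |
| Visit windows | The first post-baseline window is "Visit 2/Week 2/Day 8: Day 2 to Day 11", which straddles the nominal first blinded infusion at Week 2, so it does not separate the phases |
| Stated reason for treating laboratory data differently | None in section 5 |
| Laboratory sampling times | Not in the SAP; 2.2.1 refers to the protocol for the schedule |

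The rule as written therefore includes such samples. Whether any exist cannot be settled from the SAP.

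**Illustration of size.** The SAP gives no laboratory abnormality rate, so there is no stated figure to reproduce. Its one design calculation (80% power for the primary endpoint) does not bear on this point. All rates below are assumptions.

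- q = probability of an out-of-range value between the lead-in and the first blinded infusion, the same in both arms because randomization follows the lead-in
- p = probability of an out-of-range value after the first blinded infusion: 10% on placebo, 30% on levosimendan
- The two are taken as independent within a subject

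Under the SAP's rule a subject is counted with probability 1 − (1 − q)(1 − p). The arm difference is then (1 − q) × (0.30 − 0.10).

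For q = 10%: placebo 1 − 0.90 × 0.90 = 19%; levosimendan 1 − 0.90 × 0.70 = 37%; difference 0.90 × 20 = 18 points.

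| q (assumed) | Placebo | Levosimendan | Difference | Ratio | Expected subjects of 18 per arm |
|---|---|---|---|---|---|
| 0% | 10% | 30% | 20 points | 3.0 | 1.8 vs 5.4 |
| 10% | 19% | 37% | 18 points | 1.95 | 3.4 vs 6.7 |
| 20% | 28% | 44% | 16 points | 1.57 | 5.0 vs 7.9 |
| 30% | 37% | 51% | 14 points | 1.38 | 6.7 vs 9.2 |

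**Dependence on the independence assumption.** The factor (1 − q) holds only under independence. Take q = 10%:

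- If the lead-in abnormalities fall entirely within the blinded-phase abnormalities in both arms, the counts stay at 10% and 30%, and nothing is lost.
- If that overlap is complete on levosimendan but the phases are independent on placebo, the counts are 19% and 30%, and the difference falls to 11 points.

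**Set against sampling error.** With 18 per arm, the standard error of a 10% versus 30% difference is √[(0.10 × 0.90 + 0.30 × 0.70)/18] = √(0.30/18) = 12.9 points. The 95% half-width is about 25 points. The 2 to 6 points lost in the table correspond to 0.02 × 18 = 0.4 to 0.06 × 18 = 1.1 subjects.

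**The case against.** The strongest reply is that the problem may never arise. The SAP gives no laboratory sampling times, and some other safety measures are sparse: section 3.6.4 summarizes ECGs at baseline and Week 6 or early termination, and section 3.6.5 summarizes cardiac monitoring at baseline and Week 5. If laboratory sampling is similar, no sample falls in the lead-in interval and the counts are unaffected. This stands, and it makes the point conditional.

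It can also be said that the rates are assumed, that the shrinkage is small beside sampling error, and that the lead-in contribution is equal in expectation across randomized arms, so the effect is dilution and not bias toward one arm. All of this stands. The table carries no test, threshold or decision. The subject listings in section 6 are sorted by visit date, so the timing of a value can be recovered. They do not correct the by-arm counts, though, and section 3.6.2 does not say that its summaries are by visit, as section 3.6.3 does for vital signs.

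A reader might infer that levosimendan causes the extra placebo abnormalities and that the table hides a laboratory safety signal. The SAP supports neither. It gives no laboratory rate for any phase. The rule also does not require a normal baseline, so an abnormality that was present before any study drug and persists is counted in both arms regardless of treatment.

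**Conclusion.** The point holds in a limited, conditional form. By its own definitions, the SAP assigns any out-of-range value seen between the lead-in infusion and the first double-blind infusion to the blinded arm, placebo included. This is inconsistent with its handling of adverse events, and nothing else in the SAP corrects it.

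If such samples exist, the rule can raise the rates in both arms and can dilute the difference between them, by a factor of about (1 − lead-in rate) if the phases are independent. On assumed rates of 10% versus 30%, that is 19% versus 37% at a 10% lead-in rate and 37% versus 51% at a 30% lead-in rate. These figures rest on invented rates and on independence; they show the mechanism and do not forecast its size. The display is descriptive and neither arm is favoured in expectation. The case for changing it rests on consistency and very low cost, not on a demonstrated distortion.

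**What to change.** Add one sentence to section 3.6.2 that applies the section 3.6.1 cut-point. In the by-arm table, count only observations taken after the start of the first double-blind infusion. Report observations between the lead-in infusion and that time in a separate lead-in table. The sentence should also say how a sample is assigned if it was taken on the day of the first double-blind infusion and no time was recorded.

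The cost is one sentence and one extra table, with no new data. The change does not remove abnormalities already present at baseline, nor lead-in abnormalities that persist into later samples; both would still be counted in the by-arm table.

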2.2.3 Sample Size Calculation and Power Considerations

The sample size was estimated for the primary comparison of levosimendan and placebo using SAS (v9.4) for windows procedure PROC POWER.

A total of 36 randomized subjects (at 1:1 levosimendan vs. placebo) will provide 80% power to detect the difference at two-sided 0.05 level, assuming a standard deviation (SD) of 5 mmHg in PCWP and a treatment difference of ≥ 4.9 mmHg.

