3.4.2 Secondary Efficacy Endpoints

The secondary efficacy analyses will be performed on the Full Analysis Set.

Analyses of hemodynamic endpoints will be performed using the same ANOVA model as the primary endpoint. Series Plots will be provided for PCWP by position and visit.

Patient global assessment (based on a six-point Likert scale) at Week 6 will be performed by a Mann-Whitney-Wilcoxon test for each of the six symptom's grade. Total score will be calculated as the sum of all 6 scores for the subjects with all 6 scores available.

6MWT exercise distance at Week 6 will be tested using the same ANOVA model as the primary endpoint.

Physician's assessment of New York Heart Association (NYHA) functional class (Class I to IV) will be summarized at each time point by treatment group as a shift table from baseline to post-baseline time point. Percentages will be based on the number of subjects with both a baseline and post-baseline (at the specific time point) assessment. The treatment difference of physician's assessment of functional class at Week 6 will be tested using the two-sided Pearson's chi-squared test.

The incidence of death and hospitalization will be summarized by treatment group. Two-sided 95% CIs for the observed difference in clinical events: death and hospitalizations between the treatment groups will be presented based on a continuity-correct Z-statistic. A by-subjects listing of subjects who died due to any cause will be provided.

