3.6.5 Cardiac Monitoring

Selected cardiac monitoring parameters will be summarized using descriptive statistics at baseline and Week 5 for the treatment group. Shifts from baseline to Week 5 will be presented for the clinical alert findings by treatment group and total.

All Cardiac monitoring data will be listed by subject.

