6 PROGRAMMING SPECIFICATIONS

Analyses will be performed using SAS® version 9.3 or higher. All available data will be presented in subject data listings which will be sorted by subject and visit date as applicable. Detailed Programming Specifications will be provided in a separate document.

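### The laboratory out-of-range count takes no account of baseline status, and no shift table separates persistent pre-drug abnormality from new abnormality

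*SAP*

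**What the plan says.** SAP section 3.6.2 plans two laboratory summaries. The first is continuous: "Summary statistics will be provided for laboratory values as well as their changes from baseline for all laboratory parameters by treatment group". The second is the only categorical one, a count and percentage per parameter, by treatment group and in total, of "subjects with any post-baseline observation that is below the lower limit of normal (<LLN) or above the upper limit of normal (>ULN").

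Section 3.1.2 places baseline before any drug: "Baseline is defined as the value obtained prior to lead-in study drug infusion on Visit 1". Section 3.6 sets the grouping for all safety output: "Safety data will be summarized by actual treatment received (and in total for selected analyses) in the double-blind phase based on the Safety Analysis Set".

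No section restricts the laboratory count to subjects in range at baseline, defines a new laboratory abnormality, or plans a laboratory shift table. The SAP does plan shifts elsewhere. Section 3.4.2 presents functional class as a "shift table from baseline to post-baseline time point", and section 3.6.5 states: "Shifts from baseline to Week 5 will be presented for the clinical alert findings by treatment group and total". Section 6 adds listings: "All available data will be presented in subject data listings which will be sorted by subject and visit date as applicable".

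**The concern.** A reader takes a table of post-baseline out-of-range values by arm as a picture of what happened after dosing. Under this rule it mixes two groups: subjects out of range before the lead-in infusion who stayed out of range, and subjects who crossed a limit afterwards. Only the second group bears on drug safety, and the table does not show how large it is.

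Two things follow. Persistent abnormality adds a similar amount to both arms, so the contrast in new abnormalities looks smaller in percentage points and in ratio. And if one arm happens to start with more out-of-range subjects, the table shows a difference that no drug caused.

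Safety is part of the primary objective (section 2.1.1). Section 2.2.1 names rising blood urea nitrogen and serum creatinine among the signs of hypovolemia, so these are parameters where a reader would want to see new abnormality.

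**Working it through.** **Arm size.** The SAP states no laboratory rate. Its only design figure is the sample size: "A total of 36 randomized subjects (at 1:1 levosimendan vs. placebo) will provide 80% power to detect the difference at two-sided 0.05 level". A two-sample t-test with 18 per arm, difference 4.9 mmHg and SD 5 mmHg has power 81.5% (79.1% with 17 per arm), so the figure reproduces. It enters below only as the arm size of 18.

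**Formula.** Let b be the share of an arm out of range at baseline, r the share of those with at least one later out-of-range value, and q the rate of new abnormality among subjects in range at baseline. The planned table shows

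P = b·r + (1 − b)·q.

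If b and r are equal in both arms, the term b·r cancels:

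difference = (1 − b)·(q_levosimendan − q_placebo).

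The shrinkage does not depend on r.

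**Illustration 1** (assumed: q = 5% placebo, 30% levosimendan, r = 1).

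| b | Placebo | Levosimendan | Difference |
|---|---|---|---|
| 0% | 5% | 30% | 25 points |
| 20% | 0.20 + 0.80 × 0.05 = 24% | 0.20 + 0.80 × 0.30 = 44% | 20 points |
| 40% | 0.40 + 0.60 × 0.05 = 43% | 0.40 + 0.60 × 0.30 = 58% | 15 points |
| 60% | 0.60 + 0.40 × 0.05 = 62% | 0.60 + 0.40 × 0.30 = 72% | 10 points |

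**Illustration 2** (assumed: q = 10% placebo, 30% levosimendan, r = 0.9). Among subjects in range at baseline the difference is 20 points and the ratio 3.0.

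| b | Placebo | Levosimendan | Difference | Ratio |
|---|---|---|---|---|
| 10% | 18% | 36% | 18 points | 2.0 |
| 30% | 34% | 48% | 14 points | 1.4 |
| 50% | 50% | 60% | 10 points | 1.2 |
| 70% | 66% | 72% | 6 points | 1.1 |

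**Who is counted.** The share of counted subjects already abnormal before drug is b·r/P. In illustration 1 at b = 20% it is 0.20/0.24 = 83% for placebo and 0.20/0.44 = 45% for levosimendan. In illustration 2 at b = 30% it is 0.27/0.34 = 79% and 0.27/0.48 = 56%.

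**Chance imbalance.** With 18 in an arm, swapping one subject in range at baseline for one out of range changes that arm's expected percentage by (r − q)/18. With r = 1 this is 0.95/18 = 5.3 points at q = 5% and 0.70/18 = 3.9 points at q = 30%. The bound is 1/18 = 5.6 points.

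**Denominators after restriction.** At b = 60%, 18 × 0.40 = 7.2 subjects per arm remain.

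**The case against.** The best defence is that section 3.6.2 misstates nothing. It describes a count of out-of-range values after baseline, does not call them new, and attaches no test or decision to them. The shift tables elsewhere break no convention: one covers an efficacy endpoint, the other clinical alert findings, and the ECG interpretation in section 3.6.4 is also summarised by counts with no shift stated. Changes from baseline are planned for every laboratory parameter, so a general rise in creatinine would show there, and the listings allow case review.

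This lowers the priority but does not close the gap. Group summaries of change do not say how many subjects newly crossed a limit, and rebuilding that from listings is not a planned summary.

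Four stronger readings are tempting and are not supported:

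- **The table mostly reports disease present at entry.** The SAP gives no baseline laboratory rates, and the share varies by parameter. At b = 20% in illustration 1, under half of the counted levosimendan subjects (45%) were abnormal beforehand.
- **Every subject abnormal at baseline is counted.** Those whose later values are all in range are not. The mixing concerns persistent abnormality.
- **Excess cases are lost.** In expectation they are not. At b = 40%, 15% of 18 and 25% of 10.8 are both 2.7 subjects. What is lost is the clarity of the contrast, and noise from baseline imbalance is added.
- **One extra baseline-abnormal subject always adds 5.6 points.** That is an upper bound at 18 per arm. Eighteen is the target for completers. The Safety Analysis Set keeps dosed subjects who are later replaced, so arms can be larger.

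**Conclusion.** The concern holds as a weakness in a descriptive safety table. The stated rule combines persistent pre-drug abnormality with new abnormality, and no other planned laboratory summary separates them. With equal b and equal persistence across arms, the contrast shrinks by the factor (1 − b). This factor is exact under those assumptions, but the point figures rest on assumed rates. For a parameter that is rarely abnormal at entry the effect is negligible, and at b = 0 the planned and baseline-conditioned counts agree.

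Priority is low to moderate. The primary analysis is untouched, and the change-from-baseline summaries and listings are a partial safeguard.

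**What to change.** In section 3.6.2, keep the existing count and show values below the lower limit and above the upper limit separately. For each parameter, add by treatment group:

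- a shift table (low, normal, high) from baseline to worst post-baseline value;
- for each limit, the number of subjects not beyond it at baseline who later cross it. The denominator is subjects not beyond that limit at baseline who have at least one post-baseline value.

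The new count should not replace the existing one. Replacement would drop subjects already abnormal at entry who worsen, and the shift table would show a further rise only as high to high. That worsening stays visible through the retained change-from-baseline summaries and listings.

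The cost is SAP wording and extra table programming, with no new data. The drawback is precision. Where many subjects are abnormal at entry the denominators can fall well below arm size: about 7 of 18 at b = 60%, where one subject moves the percentage by about 1/7 = 14 points. Counts should therefore be shown beside percentages.
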